8.2.6 Serious Adverse Event Reporting by the Coordinating Center

The designated UC CCC Regulatory Manager will notify all participating sites of all unexpected and serious adverse reactions that occur on this clinical trial and which are reported to the FDA and/or UC Institutional Review Board (IRB). When reported to the FDA, a copy of the completed Form 3500A (MedWatch) will be provided to the responsible Regulatory Manager by the CCTO IND Coordinator for distribution to all participating sites.

8.2.7 Serious Adverse Event Reporting to Merck

Any serious adverse event reported to the UC CCC, whether or not related to Merck product, must also be reported within 2 working days to Merck Global Safety.

Non-serious Events of Clinical Interest will be forwarded to Merck Global Safety and will be handled in the same manner as SAEs.

SAE reports and any other relevant safety information are to be forwarded to the Merck Global Safety [contact].

The University of Chicago coordinating center staff will be responsible for reporting all events to Merck.

8.2.8 Serious Adverse Event Reporting to Evelo (Sarah Cannon Safety Department)

Any serious adverse event reported to the UC CCC, whether or not related to Evelo product, must also be reported within 2 working days to Sarah Cannon Development Innovation Safety Department.

Non-serious Events of Clinical Interest will be forwarded to Sarah Cannon Development Innovation Safety Department and will be handled in the same manner as SAEs.

SAE reports and any other relevant safety information are to be forwarded to Sarah Cannon Development Innovation Safety Department.

Safety Dept. [contact]

Safety Dept. Email: [contact]

The University of Chicago coordinating center staff will be responsible for reporting all events to Sarah Cannon Development Innovation Safety Department.

9.0 DATA REPORTING

Data reporting will be performed utilizing the eVelos electronic data capture system. The University of Chicago CRA will provide you with the applicable user registration information.

All required data must be recorded in the eVelos database at the completion of each cycle. AEs are to be entered in real time. SAEs are to be entered on the Serious Event Form within 24 hours of the site's knowledge of the event and sent via email (preferred) or fax to the

University of Chicago ([contact] or [contact]; [contact]). All case report forms must be completed by designated study personnel. Each screened (consented) patient is to be entered into eVelos within 48 hours of patient registration. In addition to direct data entry, sites may be required to provide supporting source documentation. Source records are original documents, data, and records (e.g., medical records, raw data collection forms, pharmacy dispensing records, recorded data from automated instruments, laboratory data) that are relevant to the clinical trial. Each site will prepare and maintain adequate and accurate source documents. These documents are designed to record all observations and other pertinent data for each subject enrolled in this clinical trial. Source records must be adequate to reconstruct all data transcribed onto the case report form.

10.0 STATISTICAL ANALYSIS PLAN

10.1 Statistical Analysis Plan

For purposes of analysis, the following populations are defined:

Population	Description
Enrolled	All participants who sign the ICF.
Safety	All participants who take at least 1 dose of study intervention.
Evaluable	All participants and who had no important protocol deviations affecting efficacy variables.

Hypothesis: Modulation of the gut microbiota with EDP1503 will augment the depth of response or response rate in patients with advanced melanoma who are naïve or refractory to anti-PD1 antibody.

The study will have two cohorts of subjects including:

- 1. Subjects with advanced melanoma who are naïve to anti-PD1 antibody.
- 2. Subjects with advanced melanoma who are refractory to anti-PD1 antibody.

Cohort one will employ a single stage design while cohort two will employ a Simon two stage design in which subjects will be treated with pembrolizumab in combination with EDP1503.

Cohort 1: Subjects with melanoma who are naive to anti-PD1 antibody:

Given the robust activity of pembrolizumab in patients with melanoma naïve to anti-PD1 monotherapy, we have proposed "deep response" (>80% tumor reduction) as the primary response endpoint in the frontline setting for cohort 1. This was based on the experience described of anti-PD1 antibody (nivolumab) in combination with anti-CTLA4 antibody (ipilimumab) in which approximately 40% of patients had >80% tumor reduction as best overall response^{25,29-31}. Utilizing this response endpoint as opposed to the RECIST response definition of 30% tumor shrinkage will allow the sample size to be reduced and thus facilitate a more rapid completion of the trial.

The primary efficacy endpoint of cohort 2 will be RECIST response rate. Given that response would not be expected in subjects with prior progression on anti-PD1, we will consider a response rate of 0.05 as not promising and 0.20 as promising. The type I error rate is set at 0.1 and the type II error rate at 0.1. A total of 35 subjects would be proposed. In an optimal Simon two stage design, 1 response in 20 subjects would be required in the first stage and 4 or more responses observed in 35 total subjects the combination would be deemed of substantial interest in the treatment of patients with PD1 refractory melanoma, given that the EDP1503 safety is also established (co-primary objective). A chi-squared test will be performed for the responder rate, and a 95% confidence interval may be produced, if deemed appropriate. However if any responses are observed detailed investigation of changes in the microbiome and tumor microenvironment will be indicated. The probability of stopping this cohort early is 42% if the true response rate is only 0.05.

Description of secondary and correlative endpoints will be the same as cohort 1.

Hypothesis: EDP1503 monotherapy will demonstrate a similar safety and tolerability profile to probiotics though may be associated with low grade nausea, vomiting, and abdominal pain.

The study will have two cohorts of subjects with a monotherapy run-in with EDP1503 as described earlier. There will be 2 analyses of safety across this study:

- 1. EDP1503 monotherapy run-in
- 2. Overall safety for the combination of pembrolizumab and EDP1503

All safety analyses will be performed on the Safety Population.

The co-primary endpoint for this study is the incidence of SAEs and AEs during the monotherapy run-in with ED the monotherapy period with EDP1503.

All AEs will be coded using the latest available version of the Medical Dictionary for Regulatory Activities (MedDRA) and categorized by intensity (mild/moderate/severe). Treatment-emergent AEs and SAEs will be listed and summarized by treatment period and participant population, system organ class and preferred term.

Definition of Dose Limiting Toxicity: Any toxicity of >=Grade 3, any autoimmune toxicity >CTCAE Gr 2; DLT observation period is for the length of monotherapy for each cohort. The first three patients enrolled will successively complete their 2 week DLT period prior to initiation of the subsequent patients.

Safety laboratory measurements: These variables will be listed and summarized by treatment group and participant population.

Statistical analysis of tumor biopsies

Monotherapy with pembrolizumab is associated with an approximately 40% response rate in therapy naive patients. Morphologic predictors of response include expression of PDL-1, an interferon gamma target indicative of an active inflammatory response to tumor, and the presence of tumor infiltrating CD8 T cells, dendritic cells, and NK cells of particular phenotypes. The therapeutic hypothesis of EDP1503 is that it will either induce or augment an antitumor inflammatory response, and/or will induce production of neoantigen presenting MHC class I in the tumor.

The primary goal of the biopsy analysis is to determine whether the tumor has sustained an infiltration by innate and adaptive immune cells, and/or increased tumoral expression of antigen expression apparatus such as components of MHC Class I, consistent with the therapeutic hypothesis. The secondary goal is to determine whether either the baseline level of inflammatory infiltrate or the level induced by EDP1503 treatment is predictive of immediate an extended response to the combination of EDP1503 with pembrolizumab.

The primary assays for analysis of the paired biopsies are the Nanostring IO 360 assay, an extensively validated transcript profiling assay used for semi-quantitative cell enumeration and transcriptional response in biopsies (Danaher *et al.*), as well as immunofluoresence based direct enumeration of immune cells and their spatial co-localization.

The primary hypothesis for statistical analysis of the paired biopsies is to accept or reject the hypothesis that the tumor inflammation signature (TIS, or T cell-inflamed GEP), a function calculated from the abundance of 18 transcripts detected in the sample (Table below), has changed in the tumor due to therapy. This function is highly correlated with pembrolizumab treatment outcome (Ayers *et al.*).

Table: 18 component transcripts of the TIS score

TIGIT	PD-L1	PSMB10	STAT1
CD27	CXCR6	IDO1	HLADRB1
CD8A	CMKLR1	CXCL9	HLAE
PD-L2	NKG7	HLADQA1	
LAG3	CCI5	CD276	

The variance of baseline data due to sampling variation is provided by published studies on the variability of the TIS due to sampling (Walldren *et al.*) From the dataset of multiple samplings of a baseline sample, a ratio of paired baseline TIS scores (n=85) was calculated, median (IQR): 0.9 (.25). To determine whether a difference in TIS score from day 14 to baseline is statistically significant from replicate TIS measurements, a 95% Bca confidence interval was constructed from 10000 bootstrap replicates using the ratios of paired baseline TIS scores, (0.81,1.31). Based on this estimate, a TIS ratio score > 1.31 would suggest a significant result at the 95% confidence level.

Association of the TIS with response rate (either deep response of > 80% in Cohort 1 or RECIST response rate in Cohort 2) and PFS will be analyzed following the established methods of (Ayers *et al.*).

Several outcomes may be envisaged:

- EDP1503 causes increase in TIS in a subset of patients and that increase is associated with an increase in RR and PFS.
- Baseline TIS is associated with PFS, and changes induced by EDP1503 treatment are not associated with changes in RR and PFS.
- EDP1503 does not affect TIS in any patient.

These hypotheses will be explored using linear mixed effects models fitted to immunological parameters and related composite scores to determine associations of rate of change with treatment outcome, following the strategy of Ribas *et al*.

We will also perform additional exploratory analyses.

In addition to the TIS, the IO360 panel provides for the individual semi-quantitative enumeration of multiple cell types including NK, DC, and T cells, which will be enumerated in pre and post treatment biopsies.

The immunofluorescense assays will additionally provide quantitation of immune cell types. The ability to sample multiple portions of each pre and post treatment sample with IF will allow for high-dimensional resolution of group differences determined by Wilcoxon rank-sum test. These results will be cross correlated with the Nanostring analysis, and the quality of the correlation compared to Ribas *et al*.

References:

Danaher P et al. Gene expression markers of Tumor Infiltrating Lymphocytes. JITC 5:18-33 (2017)

Ayers *et al.* IFNg related mRNA profile predicts clinical response to PD-1 blockade. JCI 127(8):2930-2940 (2017)

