1.0 TRIAL SUMMARY

Abbreviated Title	Phase 2 study of Pembrolizumab + EDP1503
Trial Phase	Phase 2
Clinical Indication	Melanoma
Trial Type	Interventional
Type of control	Internal
Route of administration	IV and oral
Trial Blinding	NA
Treatment Groups	Anti-PD1 Treatment naïve and refractory melanoma
Number of trial subjects	Minimum: 55, Maximum: 70
Estimated enrollment period	18 – 26 months
Estimated duration of trial	50 months
Duration of Participation	Up to 2 years
Estimated average length of treatment per patient	3 months

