10.2 Sample Size and Expected Accrual

The study will be conducted through the University of Chicago Personal Cancer Care Consortium which includes both sophisticated private practices as well as collaborating academic centers. Patient accrual through this mechanism would be projected to be 3 subjects per month. Cohort 1 and Cohort 2 will enroll 35 evaluable patients each.

See section 10.1 for the description of the sample size.

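### Cohort 2's two-stage rule stops an inactive combination 36% of the time, not the stated 42%, and it is not Simon's optimal design

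*Combined protocol and SAP*

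**What the plan says.** Section 10.1 (Statistical Analysis Plan, Cohort 2) sets the hypotheses: "we will consider a response rate of 0.05 as not promising and 0.20 as promising". The error limits follow: "The type I error rate is set at 0.1 and the type II error rate at 0.1". On size, "A total of 35 subjects would be proposed".

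The first-stage rule reads: "In an optimal Simon two stage design, 1 response in 20 subjects would be required in the first stage". The final rule is that with "4 or more responses observed in 35 total subjects the combination would be deemed of substantial interest". The paragraph closes with the operating characteristic at issue: "The probability of stopping this cohort early is 42% if the true response rate is only 0.05".

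Two other places bear on the first-stage size. Section 1.0 (Trial Summary) gives the number of subjects as "Minimum: 55, Maximum: 70". Section 10.2 states that "Cohort 1 and Cohort 2 will enroll 35 evaluable patients each".

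**The concern.** A first stage of 20 with a stop at zero responses has a stopping probability that can be checked in one line, and it is not 42%. The paragraph also uses *optimal*, which in a Simon design has a defined meaning: the smallest expected sample size under the null among designs that meet the error limits. A rule that looks only after 20 of 35 patients is late enough to make that doubtful.

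The early-stopping probability is the only futility property the plan reports for this cohort. These patients have already progressed on anti-PD1 therapy. Ethics and monitoring reviewers use that number to judge how many of them would be treated with an inactive combination. If it is too high and the design is called optimal, the protection looks better than it is.

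**Working it through.** **Inputs, all from Section 10.1 unless noted**

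- Null and target response rates: p0 = 0.05, p1 = 0.20.
- Limits: type I error 0.10, type II error 0.10. Sidedness is not stated; a one-sided exact binomial test is assumed.
- First stage n1 = 20, continue with at least 1 response, so stop at 0 of 20.
- Total n = 35, success with 4 or more responses.
- Cross-check of n1 from Section 1.0: 35 + 20 = 55 (minimum) and 35 + 35 = 70 (maximum). Both match, so 20 is the intended first stage.

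**Step 1. Attempt to reproduce the 42%**

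Probability of early termination = P(0 responses in 20 at p = 0.05) = 0.95^20 = **0.3585**.

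Other readings:

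| Reading | Stopping probability at 0.05 |
|---|---|
| Stop at 0 of 20 (as written) | 0.358 |
| Stop at 1 or fewer of 20 | 0.736 |
| Stop at 0 of 20, Poisson approximation, e^(-1) | 0.368 |
| Stop at 0 of 20, normal approximation without / with continuity correction | 0.152 / 0.304 |
| Stop at 0 of 17 | 0.95^17 = 0.418 |

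Nothing tried with 20 patients gives 42%. The value matches a first stage of 17, but neither document mentions one, and a first stage of 17 would make the trial minimum 35 + 17 = 52 rather than 55.

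**Step 2. Expected sample size under the null**

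E(N) = n1 + (1 - stopping probability) × (n - n1) = 20 + 0.6415 × 15 = **29.6**.

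**Step 3. Error rates of the rule as written**

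The two-stage rule rejects whenever 35 patients give 4 or more responses, except when the first 20 give none. So

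P(success) = P(X ≥ 4 | 35, p) - P(X = 0 | 20, p) × P(X ≥ 4 | 15, p).

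- At p = 0.05: 0.0958 - 0.3585 × 0.0055 = **0.094**, below the 0.10 limit.
- At p = 0.20: 0.9395 - 0.0115 × 0.3518 = **0.935**, above the required 0.90.

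**Step 4. What the optimal and minimax designs are**

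An exhaustive search over two-stage designs with n up to 60, at p0 = 0.05, p1 = 0.20 and both errors at most 0.10, gives:

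| Design | Stop at | Succeed at | Early stop at 0.05 | E(N) at 0.05 | Type I error | Power |
|---|---|---|---|---|---|---|
| Optimal | 0 of 12 | ≥4 of 37 | 0.540 | 23.5 | 0.093 | 0.902 |
| Minimax | 0 of 18 | ≥4 of 32 | 0.397 | 26.4 | 0.072 | 0.901 |
| Plan as written | 0 of 20 | ≥4 of 35 | 0.358 | 29.6 | 0.094 | 0.935 |

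The expected sizes check by hand: 12 + 0.4596 × 25 = 23.5 and 18 + 0.6028 × 14 = 26.4. The plan's design is neither optimal nor minimax. It enrols on average 29.6 - 23.5 = 6.1 more patients under the null than the optimal design.

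**The case against.** The best defence is that little depends on the number. The 42% does not enter the sample size, the decision rule or any analysis, and the rule as written meets its error limits. No efficacy conclusion would change. That is right, and it bounds the consequence. It does not make the figure correct.

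Second, 5% is the boundary of no interest, while Sections 4.2.3 and 10.1 expect essentially no responses in this population. At lower true rates the rule stops more often: 0.98^20 = 67% at 2%, 0.99^20 = 82% at 1%, and always at 0%. This is a fair point about practical futility protection. But the plan's sentence is about a true rate of 0.05, and at that rate it is wrong.

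Third, Simon designs are often written r1/n1, so the first-stage wording could be a garbled r1 = 1, meaning stop at 1 or fewer of 20. That version also meets the limits (type I error 0.080, power 0.901), and its expected sample size is 20 + 0.2642 × 15 = 24.0, close to the optimum. The text says 1 response is required, which favours continuing at exactly 1. The alternative would put early stopping at 74%, further from 42%. The stated figure is therefore wrong either way, but the ambiguity is a reason to spell out the stopping rule when correcting it.

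Fourth, a two-stage design need not be optimal or minimax. Agreed: only the label is at fault. An earlier look has its own price. A first look at 13 with the same final rule would raise early stopping at 5% to 51%, but would lower power to 0.903 and raise the chance of stopping a promising regimen at stage one from 0.8^20 = 1.2% to 0.8^13 = 5.5%. That is a trade-off for the sponsor, not a correction.

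**Conclusion.** The point holds; the text is wrong as written in two respects. The early-stopping probability at a 5% response rate is 35.8%, about 6 percentage points below the stated 42%, so an inactive combination goes on to full enrolment 64% of the time rather than 58%. The design is also not Simon's optimal design for the stated inputs: its expected sample size under the null is 29.6 against 23.5.

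The 36% and 29.6 rest on n1 = 20, which Sections 10.1 and 1.0 both support, and on stopping only at 0 of 20, which is the literal reading. The finding that 42% is wrong does not depend on which stopping threshold was meant. Why 42% was written cannot be established from the documents. The sample size and the final success rule are unaffected.

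**What to change.** In the Cohort 2 paragraph of Section 10.1:

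1. State the interim rule outright: the cohort stops if there are 0 responses in the first 20 patients and continues with 1 or more. The sponsor should confirm that this is the intended rule.
2. Replace 42% with 36%.
3. Add the expected sample size under the null, 29.6, together with the exact type I error (0.094) and power (0.935).
4. Delete the word optimal and call it a Simon-type two-stage design.

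The enrolment range in Section 1.0 can stay. If the sponsor says that stopping at 1 or fewer was intended, the figures become 74%, 24.0, 0.080 and 0.901, and the interim wording must change to match.

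The cost is a wording correction, with no extra patients and no change to the success rule. The only loss is that the reported futility protection looks less favourable.

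### The only decision rule for the primary paired-biopsy hypothesis, a TIS ratio above 1.31, is an external bootstrap limit with no stated unit or no-change centre, and no analysis tests TIS change in the trial's own pairs

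*Combined protocol and SAP*

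**What the plan says.** Section 10.1, under the statistical analysis of tumor biopsies, sets a primary hypothesis to be accepted or rejected: that the TIS "has changed in the tumor due to therapy". The therapeutic hypothesis behind it has a direction: for EDP1503, that "it will either induce or augment an antitumor inflammatory response".

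The variance comes from published work on sampling variability, not from the trial. The replicate data are described as follows: "From the dataset of multiple samplings of a baseline sample, a ratio of paired baseline TIS scores (n=85) was calculated, median (IQR): 0.9 (.25"). From these, "a 95% Bca confidence interval was constructed from 10000 bootstrap replicates using the ratios of paired baseline TIS scores, (0.81,1.31"). The plan then states: "Based on this estimate, a TIS ratio score > 1.31 would suggest a significant result at the 95% confidence level".

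Three outcomes are envisaged. One is that "EDP1503 causes increase in TIS in a subset of patients"; another is that "EDP1503 does not affect TIS in any patient". The mixed-effects models that follow are fitted "to determine associations of rate of change with treatment outcome". The Wilcoxon rank-sum test is for the immunofluorescence data.

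Section 3.3 lists the effect on the tumor microenvironment as an exploratory objective.

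**The concern.** A confidence interval for a summary of replicate ratios says how precisely that summary is known. It is not a range within which one patient's ratio should fall when nothing has changed. Nor is a fixed external cut-off a valid test of a cohort average, because it ignores the variance and the number of the trial's own pairs.

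The plan does not say whether 1.31 applies to a patient or to a cohort, which statistic was bootstrapped, or what ratio counts as no change. Two analysts could follow the text and reach different conclusions. The other listed analyses do not fill the gap: the mixed models look for association with outcome, and the rank-sum test concerns immunofluorescence measurements. So the hypothesis that patients undergo a second biopsy to address has no test based on those biopsies.

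**Working it through.** **Inputs.** From Section 10.1: n = 85 replicate ratios, median 0.9, IQR 0.25, interval (0.81, 1.31), cut-off 1.31. From Section 10.2: 35 evaluable patients per cohort. My assumptions: 25-35 usable pairs, since Section 4.2.3.2 lets the cohort 1 second biopsy be omitted when not clinically feasible; normal or log-normal replicate ratios; log-SD of trial pairs 0.23 (slightly above the replicate value below) or 0.4 (allowing for extra variation between biopsies).

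**1. Can the printed interval be reproduced?** Normal SD = 0.25/1.349 = 0.185. Log-normal sigma = asinh(0.125/0.9)/0.6745 = 0.205. The printed width is 1.31 − 0.81 = 0.50.
- *CI of the mean:* expected width 2 × 1.96 × 0.185/√85 = 0.08. A width of 0.50 needs SD = 0.50 × √85/3.92 = 1.18, about six times 0.185. One extreme value could come close: a constructed set of 85 ratios with median 0.9, IQR 0.25, a wide lower tail and a single ratio of 8 gave a BCa interval of (0.84, 1.30).
- *CI of the median:* expected width about 0.08 × 1.253 = 0.10. The limits sit near ranks 33 and 53 of 85, inside the quartiles (near ranks 22 and 64). Limits of 0.81 and 1.31 would force an IQR of at least 0.50, against 0.25 printed. This is impossible whatever the shape.
- *2.5-97.5% range of single ratios:* normal 0.9 ± 1.96 × 0.185 = (0.54, 1.26); log-normal 0.9 × exp(± 1.96 × 0.205) = (0.60, 1.35). The upper end fits and the lower end does not. If 0.81 were the 2.5% point, the lower quartile would be at least 0.81 and the upper at least 1.06. The upper quartile gap (at least 0.16) would then be at least 1.8 times the lower (at most 0.09), which is strong right skew. A range of this kind would also not be a BCa confidence interval.

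**2. Per-patient use.** Probability that an unchanged tumor exceeds 1.31, and expected number in 35 pairs:

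| No-change centre | Normal | Log-normal | Expected in 35 |
|---|---|---|---|
| 0.9 | z = 0.41/0.185 = 2.21, 1.3% | z = ln(1.31/0.9)/0.205 = 1.83, 3.4% | 0.5-1.2 |
| 1 | z = 0.31/0.185 = 1.67, 4.7% | z = ln(1.31)/0.205 = 1.32, 9.4% | 1.7-3.3 |

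A calibrated upper limit gives 2.5%, or 35 × 0.025 = 0.9 patients. The choice of centre is a real question: if the order within replicate pairs is arbitrary, the ratio should centre on 1, yet a median interval of about 0.85-0.95 excludes 1.

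Replicates of a baseline sample may also understate the variation between two biopsies. Section 8.1.1.11 asks for the same site only where feasible. Footnote d of the flow chart (Section 6.1) allows archival baseline tissue in cohort 1 and a second biopsy from day 4 in cohort 2, while the rule is written for day 14. If the log-SD of real pairs were 1.5 times the replicate value (an assumption), the log-normal rates would be 11% (centre 0.9) and 19% (centre 1).

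**3. Cohort-mean use.** At a true geometric mean ratio of 1.2, P(call) = P(Z > ln(1.31/1.2)/(SD/√n)), with ln(1.31/1.2) = 0.0877. The comparison is a two-sided 5% paired t-test on log ratios (noncentral t).

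| Log-SD | Pairs | Ratio > 1.31 | Paired t-test |
|---|---|---|---|
| 0.23 | 25 | 2.8% | 96.7% |
| 0.23 | 35 | 1.2% | 99.5% |
| 0.4 | 25 | 13.6% | 59.0% |
| 0.4 | 35 | 9.7% | 74.5% |

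More pairs make the fixed cut-off less likely to detect this effect. For 80% power it needs a true ratio of 1.31 × exp(0.8416 × SD/√n) = 1.35-1.36 (log-SD 0.23) or 1.39-1.40 (0.4). The paired test needs 1.12-1.14 or 1.22-1.26.

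**The case against.** The strongest reply is that nobody proposes to apply 1.31 to a cohort mean. The plan compares a day-14 to baseline difference with replicate measurements, and two of its envisaged outcomes speak of a subset of patients and of any patient. On that reading, with the printed median as centre, the cut-off is close to nominal. This largely stands. A reader might infer from the third calculation that the trial will miss a real rise in TIS, but the documents do not support that: they do not state the unit, and they lean the other way. What remains is that the per-patient error rate is undocumented, and that a hypothesis to be accepted or rejected has no rule for turning individual calls into a decision.

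A reader might also infer that the interval is proven wrong. It is not. The statistic is unnamed, the raw ratios are not in the documents, and an extreme outlier (for a mean) or strong right skew (for a range) could come close to it. Only the median reading is excluded.

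Calling increases only is defensible given the directional therapeutic hypothesis, although it does not match the wording of the hypothesis to be tested. It is also fair to say that a test of the average shift would not by itself address an effect confined to a subset. That is accepted and shapes the fix.

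**Conclusion.** The point holds as a gap in the plan, not as a demonstrated error in the likelier use of the rule. The sole criterion for the primary biopsy hypothesis is an external limit with no named statistic, unit or no-change centre, and no analysis tests TIS change in the trial's own pairs. Per patient, the false-call rate is 1.3-3.4% or 4.7-9.4% depending on the centre, under normal or log-normal shapes and replicate-level noise. The cohort-mean figures (1-3% or 10-14% against 97-99.5% or 59-75%) apply only if the rule is used that way, and depend on the assumed log-SDs of 0.23 and 0.4.

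The importance is moderate. The objective is exploratory and no efficacy, safety or stopping decision rests on it, but it is the stated primary hypothesis for the paired biopsies. The change should be made before the biopsies are analysed.

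**What to change.** - Add a paired test of log(post/pre TIS) within each cohort as the test of average change, two-sided or one-sided as pre-specified, and report the geometric mean ratio with its 95% confidence interval.
- Alongside it, keep a per-patient analysis for the subset hypothesis. Take the reference limit from the distribution of the 85 individual log ratios, not from a confidence interval for a summary. State the no-change centre, and compare the number of patients beyond the limit with the number expected by chance (35 × 0.05 = 1.75 for two-sided 95% limits, 0.9 for the upper limit alone).
- Name the statistic that was bootstrapped, and correct or explain (0.81, 1.31).

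The cost is SAP wording and a re-analysis of the existing replicate dataset, with no new samples. The number of patients called changed may rise or fall. The paired test has limited power when only some patients respond: in simulation with 35 log-normal pairs, no change at 1 and 7 patients doubling their TIS, power is about 64% (log-SD 0.23) or 34-35% (0.4); with a 1.5-fold rise in those 7 it is about 35-36% or 17%. With 20 pairs and a uniform shift, the test has 80% power for a ratio of 1.16 (log-SD 0.23) or 1.30 (0.4).
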